#### 4.6 Exclusion Criteria for Parents/Caregivers

**4.6.1** Any condition or social circumstance situation that, in the opinion of the IoR or designee, would make study participation unsafe for the caregiver or the child study participant, complicate interpretation of study outcome data, or otherwise interfere with achieving the study objectives.

#### 4.7 Co-Enrollment Considerations

Co-enrollment in other studies is allowable for parents/caregivers. For participants, co-enrollment in other studies that do not involve an investigational agent, device, or vaccine may be allowed, although careful consideration must be given to visit burden, blood draw volumes, and interpretation of outcome data across studies. Given these considerations, requests for co-enrollment must be approved in advance by teams of both studies. Requests for such approval should be emailed to the IMPAACT 2036 Clinical Management Committee (CMC).

# 4.8 Recruitment, Screening, and Enrollment Process

This section provides a description of the recruitment methods, screening and enrollment processes, and the definition of enrollment for participants.

Recruitment methods for this study may vary across sites. In general, recruitment of participants, is expected to rely on current clients being seen at a study clinic or from active identification and referral of children living with HIV-1 who are ART-experienced and virologically suppressed; participants may have acquired HIV-1 perinatally or behaviorally. Any study advertising materials must undergo approval by the sIRB (for US sites), or site IRBs/ECs (for non-US sites). Sites are encouraged to solicit input and feedback on recruitment materials from their local Community Advisory Board.

Upon identification of a potentially eligible participant, study staff will provide information about the study to the parent or legal guardian and/or the potential participant (as applicable). Each parent or legal guardian and/or potential participant (as applicable) who expresses interest in learning more about the study will be provided additional information, education, and counseling as part of the study parental permission and informed assent process. The process will include detailed review of the study parental permission and informed assent forms, time to address any questions or concerns the potential participant, parent, or legal guardian may have, and an assessment of understanding, before proceeding to parental permission and informed assent decisions. The parental permission and informed assent processes will be fully documented, consistent with the DAIDS policies referenced in Section 13.3.

Each site must establish standard operating procedures (SOPs) for eligibility determination that describe where and when screening procedures will be performed; roles and responsibilities for performing the required procedures; roles and responsibilities for assessing and confirming eligibility; and procedures for documenting the process, taking into consideration the required timing of enrollment. Sites are encouraged to minimize the time from screening to enrollment.

Eligibility screening will be initiated after written parental permission and informed assent (as applicable) is provided. The Study Enrollment System (SES) will assist in tracking of the screening process and obtaining a study-specific screening number. Screening will include confirmatory HIV-1 testing (if needed) and assessment of other entry criteria. If at any time it is determined that an individual is not eligible for the study, or that study participation may not be feasible or in the participant's best interest, the eligibility screening process will be discontinued; these individuals should be actively referred to non-study sources of care. Screening assessments, unless otherwise noted (see Section 6.2), must be completed within 28 days prior to entry. Re-screening is permitted one time and will require most screening procedures to be repeated, as specified in Section 6.1.

The IMPAACT Data Management Center (DMC) SES will be used to assist with tracking the screening and enrollment process, within and across weight bands. When parental permission and informed assent (as applicable) are obtained, a participant identification number (PID) will be assigned to the potential participant and a study-specific screening number will be obtained through the SES. For participants found to be eligible, enrollment will occur upon successful entry of

required eligibility data into the SES. Successful entry into the SES will generate a study identification number and study drug prescribing information. For potential participants found to be ineligible for the study, or who do not enroll in the study for any reason, limited demographic information and reasons for non-enrollment will be entered into electronic case report forms (eCRFs).

## 4.9 Recruitment, Screening, and Enrollment Process for Parents/Caregivers

Recruitment of parents/caregivers will generally rely on site staff identification of potentially eligible caregivers as they present to the study clinic. A brief description of the parent/caregiver component should be provided to the parent or legal guardian who is providing written parental permission for the child's study participation at the child's screening visit. The parent or legal guardian may indicate their own interest and willingness to participate or may identify a different parent/caregiver to participate in this component of the study. One parent/caregiver of each enrolled child should be approached to complete the caregiver behavioral assessments, assessed for eligibility, and enrolled if eligible (if ineligible, additional parents/caregivers may be approached/assessed for eligibility, as needed, with the goal of enrolling one parent/caregiver per child participant). Sites must source document parent/caregiver recruitment and follow their IRB/EC approved recruitment methods for approaching a potential parent/caregiver participant. Parent/caregiver recruitment, screening, and enrollment may only occur after child participant enrollment in the main study.

Parents/caregivers must provide informed consent prior to their enrollment and completion of the quantitative survey and/or qualitative interview(s). Eligibility criteria are provided in Section 4.5 and Section 4.6 and must be confirmed and source documented after obtaining informed consent. Eligibility determination for parents/caregivers must also be included in site SOPs, which describe how, where and when recruitment and confirmation of eligibility criteria will be performed; roles and responsibilities for assessing and confirming eligibility; and procedures for documenting the process.

The Data Management Center (DMC) system will not be used for tracking the parent/caregiver screening process. However, sites will source document reasons for any consenting caregiver found to be ineligible. For parents/caregivers found to be eligible, enrollment into the study will occur upon successful entry of required eligibility data into the IMPAACT DMC Study Enrollment System (SES). Successful entry into the SES will generate a study identification number (SID).

The IMPAACT 2036 MOP provides further guidance on operational and logistical considerations of assessing and confirming eligibility, and enrolling parents/caregivers to the study for completion of quantitative surveys and qualitative interviews.

# 4.10 Participant Retention

Once a participant is enrolled in this study, study staff will make every effort to retain them in follow-up for the protocol-specified duration of follow-up, thereby minimizing potential biases and loss of statistical power associated with loss-to-follow-up. Refer to Section 9.5.3 for more information on monitoring participant retention in this study.

#### 5 STUDY PRODUCT

Site pharmacists should consult the *Pharmacy Guidelines and Instructions for DAIDS Clinical Trials Networks* for standard pharmacy operations. For this study, the term study product refers to CAB (tablet, dispersible tablet, injection) and RPV (tablet, tablet which must be dispersed, injection). Refer to the Investigator's Brochure (IB) for Cabotegravir and the IB for TMC278 (rilpivirine, oral and parenteral) for further information about these study drug formulations.

# 5.1 Study Product Regimen

At Entry, all participants will discontinue their pre-study cART regimen and will be assigned to a dosing regimen based on their weight at entry to the applicable cohort. Weight-based dose adjustments will made according to guidance provided in Section 5.1.1 below. Dosing regimens may be modified following the Cohort 1 interim analyses or based on experience in the study, in which case, the new regimen will be specified per Section 5.1.2 below.

Cohort 1 participants will receive oral CAB + oral RPV followed by intramuscular CAB LA + RPV LA as shown in Table 1 (for oral dosing) and Table 2 (for LA injections).

Cohort 2a participants will receive oral CAB + oral RPV followed by intramuscular CAB LA + RPV LA. Cohort 2b participants will receive intramuscular CAB LA + RPV LA only. As described in Section 3, Cohort 2a and Cohort 2b will be opened to accrual following the Cohort 1 interim analyses and full accrual of Cohort 1. The oral and injectable dosing regimens for both Cohort 2a and Cohort 2b will also be communicated, per weight band, at that time; see Section 5.1.2 below.

Table 1.
Cohort 1: Initial Oral Lead-In Dosing Regimen

Weight Band	Daily Oral Dose (through the Week 4b visit)
Weight Band 1 35-<40 kg	30mg CAB + 25mg RPV  • Administered as one 30mg CAB tablet + one 25mg RPV tablet
Weight Band 2 25-34.9 kg	10mg CAB + 25mg RPV  • Administered as two 5mg CAB DT + one 25mg RPV tablet
Weight Band 3 20-24.9 kg	10mg CAB + 15mg RPV  ◆ Administered as two 5mg CAB DT + six 2.5mg RPV tablets
Weight Band 4 14-19.9 kg	10mg CAB + 12.5mg RPV  ◆ Administered as two 5mg CAB DT + five 2.5mg RPV tablets
Weight Band 5 10-13.9 kg	10mg CAB + 12.5mg RPV  ◆ Administered as two 5mg CAB DT + five 2.5mg RPV tablets

Table 2.
Cohort 1: Initial (Q4W) IM Injection Dosing Regimen

Confort 1. Initial (4444) in injection bosing Kegimen		
Weight Band	Q4W Long-acting IM Dose Regimen	
Weight Band 1	Initial injections (Wk 4b): 600mg CAB LA + 900mg RPV LA	
35-<40 kg	Subsequent injections (following Wk 4b), every four weeks: 400mg CAB LA + 600mg RPV LA	
	Initial injections (Wk 4b): 300mg CAB LA + 600mg RPV LA	
Weight Band 2 25-34.9 kg	Subsequent injections (following Wk 4b), every four weeks: 200mg CAB LA + 450mg RPV LA	
Weight Band 3 20-24.9 kg	Initial injections (Wk 4b): 300mg CAB LA + 600mg RPV LA	
20 24.7 kg	Subsequent injections (following Wk 4b), every four weeks: 200mg CAB LA + 450mg RPV LA	
Weight Band 4 14-19.9 kg	Initial injections (Wk 4b): 300mg CAB LA + 450mg RPV LA	
Weight Band 5 10-13.9 kg	Subsequent injections (following Wk 4b), every four weeks: 200mg CAB LA + 300mg RPV LA	

## 5.1.1 Dose Adjustments Due to Changes in Weight Band

Participant weight at the Entry visit will establish the participant's weight band and the assigned oral dosing for the full duration of the oral lead-in phase. Oral dosing will not be adjusted due to weight band changes (increases or decreases in weight) which may occur during the oral lead-in phase.

At each injection visit, participant weight will be assessed prior to administering study product to determine the appropriate weight band and injectable dosing regimen to be administered at that visit. Participants who increase in weight bands will begin the dosing regimen corresponding to their new applicable weight band. However, decreases in weight band will not result in a dose change; participants will remain on the dose regimen of the largest weight band achieved.

## 5.1.2 Dosing Regimen Modifications

Dosing regimen modifications for each weight band may occur as needed following the Cohort 1 interim analyses and/or based on ongoing reviews of safety, PK, viral load, tolerability, and all other relevant data within the study or from other ongoing studies of the study drugs in pediatric populations. If a dose modification is indicated, accrual will be paused in the relevant weight band(s) until an SMC review is convened, and the proposed dose modification is approved. Dose modifications, and the initial doses for Cohort 2 as noted above, will be selected from the tables in Appendix VII. Accrual pauses, resuming accrual, and dose modifications will be communicated to sites by Memoranda of Operational Instruction, approved by the CMC. See Section 9.5.1. Currently enrolled and newly enrolling participants will be assigned to the updated dosing regimens.

In the event of an injection regimen modification from Q4W to Q8W dosing, enrolled participants still in the oral lead-in phase will receive injections on the Q8W schedule. Enrolled participants who have initiated injections on a Q4W injection schedule and have completed the Week 12 visit will continue to receive injections on a Q4W schedule through the Week 24 (Cohort 1 and Cohort 2a) or Week 20 (Cohort 2b) visit. The Memorandum of Operational Instruction will provide additional dosing regimen transition guidance for participants already on treatment, including those who have only received the first two sets of injections of CAB LA + RPV LA (Week 4b and Week 8), at the time of any modifications. See Section 6.1.2 for more information.

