#### **Summary of Rilpivirine Drug Metabolism and Pharmacokinetics (DMPK):**

RPV LA has been administered IM to healthy adults and adults living with HIV-1 at 300 mg to 1200 mg. After IM injection of RPV LA, RPV is slowly absorbed from the injection site, exhibiting flip-flop pharmacokinetics with an apparent half-life of 200 days in adults(11).

RPV is primarily metabolised, via CYP3A, and eliminated by the liver. No dose adjustment is required in patients with mild or moderate hepatic impairment (9). Oral RPV must be taken with a

meal for optimal absorption (9). Exposure to oral RPV can be affected by modulators of CYP3A4-enzyme activity and drugs that increase gastric pH. Drugs that induce CYP3A4 activity can reduce RPV exposure and should not be co-administered. Drugs that inhibit CYP3A4 activity can increase RPV exposure but do not require dose adjustments (9). Renal elimination of RPV is negligible. Therefore, no dose adjustment of RPV is required in patients with renal impairment (9).

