#### 6.1.2 Additional Considerations for a Q8W Injection Schedule

In the event of a dosing regimen modification (see Section 5.1.2), the follow-up visit schedule for each cohort will remain per Sections 6.3 through 6.6 and per Appendix I. However, injections and other select visit procedures, as specified below, will only occur at a Q8W frequency.

Participants newly enrolling into the study on a Q8W injection schedule will have injectable study product administered at the following visits:

- For Cohort 1 (through Week 72) and Cohort 2a (through Week 48 only): Weeks 4b, 8, 16, 24, 32, 40, 48, 56, 64, and 72.
- For Cohort 2b: Entry, Week 4, and at Weeks 12, 20, 28, 36, 44.

When receiving injectable study products on a Q8W schedule, acceptability/tolerability assessments for participants and parents/caregivers and all laboratory evaluations (including urine pregnancy tests and all bloodwork) will be administered on a Q8W schedule and will only take place at injection visits. Non-injection visits for participants on a Q8W injection schedule may be conducted in person or telephonically.

See the IMPAACT 2036 MOP for further details regarding implementation of a dosing regimen modification and associated procedural changes when moving from Q4W to Q8W dosing.

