#### Potential Dose Modification

Dose adjustments for management of individual participant PK target exposures will not occur. In the event of failure with respect to safety and/or PK criteria that are deemed potentially avoidable by lower (or higher) exposure to the study drugs, as judged by the CMC, a dose adjustment will be considered for the applicable weight band. As noted in Section 5.1.2, dosing regimen modifications for each weight band may occur as needed following the Cohort 1 interim analyses and/or based on ongoing reviews of safety, PK, and all other relevant data, and will be implemented across all participants within the applicable weight band group. During the reviews of the data and based on the findings, the protocol team may decide whether to continue with Q4W dosing, move to Q8W dosing, change to a different dose on either the Q4W or Q8W schedule, or gather additional data on the initial Q4W dosing regimen for each weight band.

At the two planned interim analyses, and at any other additional relevant PK analysis, the PK parameters calculated from each individual participant will be used to predict that participant's exposure at Wk. 12 (Cohort 1) or Wk. 8 (Cohort 2b) if they were taking Q8W injections instead of Q4W (via modeling and simulation). Using the *predicted* Q8W dose interval trough concentrations from each participant, the same trough acceptance criteria will be applied as already noted in the protocol above. The same strategy will be used, if needed, during ongoing study PK analyses to assess alternate doses or dose intervals if particular weight-bands do not meet acceptance criteria for either the oral or the LA dosing. In other words, based on the observed PK data from each participant, those participants' predicted exposures on the new dose or dose regimen will be calculated, and the acceptance criteria will be applied to those individual participants' predictions on that new dose or dose interval.

When assessing whether to change the dose interval, if the median of the predicted concentrations from every 8 week dosing meets the LA dosing trough acceptance criteria, new participants in the corresponding Weight Bands may be initiated on every 8 week dosing. Ongoing study participants that enrolled on every 4 week dosing may also transition to every 8 week dosing after their week 24 visit.

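### Section 5.1.2 keeps Week 12 completers on Q4W through Week 24 (Week 20 in Cohort 2b) whatever the reason for a change to Q8W, and this does not agree with Section 10.3.1

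*Protocol*

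**What the plan says.** **Section 5.1.2.** The first paragraph lets regimens be modified after the Cohort 1 interim analyses or on ongoing review of safety, PK and other data. It ends: "Currently enrolled and newly enrolling participants will be assigned to the updated dosing regimens". The second paragraph covers a change from Q4W to Q8W. Children still in the oral lead-in go to Q8W. Those who started injections on Q4W and "have completed the Week 12 visit will continue to receive injections on a Q4W schedule through the Week 24" visit, or the Week 20 visit in Cohort 2b. A memorandum is to give further transition guidance for children already on treatment.

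**Section 10.3.1, Potential Dose Modification.** The trigger is worded: "In the event of failure with respect to safety and/or PK criteria that are deemed potentially avoidable by lower (or higher) exposure". The Clinical Management Committee (CMC) then considers an adjustment for the weight band. Modifications follow the interim analyses or ongoing reviews, with a reference back to Section 5.1.2, "and will be implemented across all participants within the applicable weight band group". The options include: "move to Q8W dosing, change to a different dose on either the Q4W or Q8W schedule". The last paragraph covers the case where predicted Q8W troughs meet the acceptance criteria. New children may then start on Q8W, and ongoing Q4W children may change over after Week 24.

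**Section 6.1.2.** After a modification the visit schedule stays the same. "However, injections and other select visit procedures, as specified below, will only occur at a Q8W frequency". The list of Q8W injection visits that follows is for newly enrolling children.

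**The concern.** The Week 24 deferral suits a change made because Q8W is predicted to be adequate, where nothing is wrong with Q4W. As worded in Section 5.1.2 it also covers a change made because exposure on Q4W is too high or its safety is unacceptable. A site would then have one instruction to move the band to the new regimen and another to keep a Week 12 completer on the old interval until Week 24.

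The interim analyses take place once at least 8 dose-evaluable children have completed Week 12, so their participants are the group the sentence addresses. The injections are depots that cannot be withdrawn. The protocol describes long-acting rilpivirine as "exhibiting flip-flop pharmacokinetics with an apparent half-life of 200 days in adults". Which sentence is followed decides how much drug these children receive between Week 12 and Week 24, within the Cohort 1 primary safety period.

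**Working it through.** **1. Is a safety failure at an interim a planned-for outcome?** Table 9 (Section 9.5.2) gives the probability that 8 dose-evaluable children fail the Safety Guidelines. With *a* the rate of related non-life-threatening Grade 3 or 4 events and *b* the rate of related life-threatening or fatal events:

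P(fail) = 1 − Σ C(8,x) aˣ (1−a−b)⁸⁻ˣ, x = 0, 1, 2

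For a = 0.25 and b = 0 this is 1 − (0.1001 + 0.2670 + 0.3115) = 0.3215, against 0.32 in the table. All eleven rows reproduce to rounding. Over-exposure is also provided for: the Week 12 trough criteria in Section 10.3.1 have upper bounds (6.7 mcg/mL for cabotegravir, 100 ng/mL for rilpivirine).

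**2. The passages by reason for the change (child past Week 12, not yet past Week 24)**

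| Passage | Change permitted by predicted Q8W troughs | Change for safety or over-exposure |
|---|---|---|
| 5.1.2, first paragraph | updated regimen | updated regimen |
| 5.1.2, second paragraph | *will* stay on Q4W to Week 24 | *will* stay on Q4W to Week 24 |
| 10.3.1, main paragraph | all participants in the band | all participants in the band |
| 10.3.1, last paragraph | *may* move after Week 24 | not addressed |
| 6.1.2, frequency statement | Q8W frequency only | Q8W frequency only |

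In the middle column a specific rule can be read as qualifying the general ones. In the right-hand column only the second paragraph of 5.1.2 keeps the child on Q4W, and nothing in 10.3.1 supports it.

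**3. Injection sets after Week 12 and through Week 24**

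- Literal 5.1.2: Weeks 16, 20, 24 = 3.
- Published Q8W visits (6.1.2): Weeks 16, 24 = 2, so the excess is 3 − 2 = 1.
- Eight weeks counted from a Week 12 injection: Week 20 = 1, so the excess is 3 − 1 = 2.

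These are for a child who has not yet reached Week 16. A child further on has fewer sets at issue.

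**4. Rilpivirine burden at Week 28.** Inputs: injection days counted from Week 4b (Appendix II); half-life 200 days (Section 1.2.2, adults); first dose 1.33 to 1.5 times later doses (Table 2: 600/450, 900/600 and 450/300). Dose amounts are assumed unchanged. Burden just before any Week 28 injection (day 168) is Σ Dᵢ × 0.5^((168 − dᵢ)/200), with later doses set to 1. The factors for days 0, 28, 56, 84, 112 and 140 are 0.5586, 0.6156, 0.6783, 0.7474, 0.8236 and 0.9075.

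| Schedule (days) | First dose 1.33 | First dose 1.5 |
|---|---|---|
| Q4W: 0, 28, 56, 84, 112, 140 | 4.517 | 4.610 |
| Week 16/24 grid: 0, 28, 56, 84, 140 | 3.694 | 3.787 |
| Next set at Week 20: 0, 28, 56, 112 | 2.862 | 2.955 |

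Against the grid the ratio is 4.517/3.694 = 1.22 or 4.610/3.787 = 1.22. Against a next set at Week 20 it is 4.517/2.862 = 1.58 or 4.610/2.955 = 1.56.

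**The case against.** Section 10.3.1 is not simply a rival rule. It refers back to 5.1.2, its phrase about all participants can be read as meaning by band rather than by child, and its last paragraph also places the change after Week 24. Section 5.1.2 can be read as a general rule followed by a specific one. The only criterion stated for changing the interval as such is the permissive PK one. All of this stands, and it settles the matter for a PK-permitted change. It does not reach a change made to lower exposure. The same subsection lists Q8W among its options there, and the deferral in its last paragraph does not extend to that case.

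The safeguards are real:

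- related Grade 3 and any Grade 4 events generally lead to a hold, and the investigator may hold at any time (8.1.1);
- product can be discontinued for the child's welfare or on new data (8.5);
- the Study Monitoring Committee (SMC) reviews any modification before it is final, and the CMC may pause dosing meanwhile (9.5.4);
- dose amounts can be changed (Appendix VII);
- the memorandum can add guidance (5.1.2).

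They limit the practical risk. None is written as an exception to the continue-Q4W sentence. Holds and discontinuation stop both drugs rather than move a child to Q8W. Individual reduction for toxicity (8.1) and individual adjustment for PK exposure (10.3.1) are both barred. A child without an event in an over-exposed band therefore depends on the band-level change.

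A reader might infer that the children whose toxicity caused the change are ordered to stay on the toxic regimen. The documents do not support that: most children with related Grade 3 or higher events would already be held or off drug, and some are dose-evaluable without reaching Week 12. A reader might also count three extra injection sets, but three is the whole Q4W count and the excess is one or two. Nor does the point undermine the primary safety estimand, whose treatment condition allows Q4W or Q8W through Week 24 (Table 5).

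**Conclusion.** The disagreement is real but narrow. It concerns children who began injections on Q4W, have completed Week 12 and are not yet past Week 24 (Week 20 in Cohort 2b), when the interval is changed for safety or exposure reasons. It matters mainly after a PK over-exposure finding.

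Literal use of 5.1.2 gives 1 to 2 more injection sets per child through Week 24. Rilpivirine burden at Week 28 is about 1.22 times that on the published grid. The figure of up to about 1.58 applies only if the next set after Week 12 were at Week 20, which is not on that grid. Both ratios assume unchanged dose amounts and the adult half-life. Higher Q8W doses would shrink the excess, and the protocol itself says absorption may be faster in children (1.3.3). No corresponding figure was worked out for cabotegravir. The textual conflict does not depend on these numbers.

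The passages should be reconciled. This review takes no view on which schedule is clinically right.

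**What to change.** In Section 5.1.2, state which kind of interval change the continue-Q4W sentence covers. Add one explicit instruction, chosen by the sponsor's clinicians, for children past Week 12 when the change is made for safety or exposure reasons. Then align the rest: *will* in 5.1.2 with *may* in the last paragraph of 10.3.1, the all-participants sentence in 10.3.1, and the frequency statement in 6.1.2.

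The cost is two or three sentences of protocol text, with no extra visits, samples or children.
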